#### 8.4 Clinical Laboratory Tests (Serum Chemistry, Hematology, Coagulation, Urinalysis)

Clinical laboratory reference ranges will be listed by laboratory group, test, sex, and age category, where appropriate.

Serum chemistry, hematology, coagulation, and urinalysis will be performed at the following time points:

**Table 8.1 Laboratory Data Time Points**

Test	Period	Day	Hour
Serum Chemistry/ Hematology/ Urinalysis	Screen		
	1	-1	Check-in
		2*	24
Coagulation	Screen		
		1	Predose, 0.083, 0.25, 0.5, 1, 2, 4
		2*	24
		14	FU
		28	FU
*Prior to discharge from CRU or at early termination from the study. FU = Follow-up			

Out-of-normal range flags (1st flag) will be recorded as follows:

- for numerical results: high (H) and low (L);
- for categorical results: did-not-match (\*).

If a value fails the reference range, it will automatically be compared to a computer clinically significant (CS) range (2nd flag).

- If the value falls within the computer CS range, it will be noted as “N” for not clinically significant.
- If the value fails the CS range, it will be flagged with a “Y” which prompts the PI to determine how the out-of-range value should be followed using 4 PI flags (3rd flag):
  - "N", not clinically significant,
  - "R", requesting a recheck,
  - "^", checking at the next scheduled visit,
  - "Y", clinically significant.

To distinguish the PI flags from the computer CS range flags, the PI flags “N” and “Y” will be presented as “-“ and “+” in the data listing, respectively.

In addition, a derived flag (a 4th flag) based on a search of the PI comments for a comment of “CS” or “Clinically Significant” will be used. The derived flag will be populated with “+” if the positive clinically significant determination is found in the comments for cases when the PI flag is populated with a “^” or a “R”.

Out-of-range values and corresponding recheck results will be listed. Out-of-range values are considered to be values that are out-of- normal range as defined by the clinical laboratory. Results that are indicated as CS by the PI (either in the PI flag or in PI comments) will be also listed in a separate table.

For all safety values that are numeric, descriptive statistics will be presented for each laboratory test by dose level, pooled placebo, and time point. Change from baseline will be summarized in a similar way. In addition, for the activated partial thromboplastin time (aPTT) (coagulation test), the fold change from baseline will be calculated and summarized in a similar way. The following formula will be used for the calculation: postdose/baseline. Baseline is defined as the result closest and prior to the dose on Day 1 (i.e., Day 1 for Coagulation and Day -1 for the rest of tests) which may include unscheduled or recheck results, whichever is later. Postdose unscheduled events or rechecks will not be included in summaries. Similarly early termination results will not be included in summaries.

For each laboratory test, a shift table will be developed to compare the frequency of the results at baseline (above normal, normal, or below normal) with the respective postdose results. For urinalysis tests, the categories are normal and outside normal.

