### **10.2.4 Follow-up Visits (Day 14 and 28)**

Subjects (including those who terminate early) will return on Days 14 and 28 for follow-up procedures (coagulation sample collection, thrombin time measurement, and immunogenicity sample collection) and to determine if any AE has occurred since the last study visit. If thrombin time and/or aPTT are found to be elevated beyond normal range (unless it is still within  $\pm 10\%$  of individual's baseline value at check-in) at Day 14, both tests will be repeated. If aPTT and/or thrombin time are elevated beyond the normal range in the retest, a mixing study will be performed. The mixing study will be performed on Day 14 by mixing the subjects' plasma 1:1 with normal human pooled plasma and thrombin time evaluated. If the thrombin time does not correct, the presence of ADA and cross-reacting prothrombin/thrombin antibodies will be presumed and will be directly assessed before dose escalation decision. The applicable subject will remain at the CRU until these test results are obtained.

Subjects who terminate the study early will be asked to continue aPTT and thrombin time monitoring as scheduled until Day 28.

Any subjects for whom aPTT and/or thrombin time did not reach  $\pm 10\%$  of the baseline value or within the normal range by Day 14, will return every 7 days ( $\pm 2$  days) until aPTT and thrombin time reach  $\pm 10\%$  of the baseline value or within the normal range and for a FU visit (i.e., follow-up procedures and AE evaluation listed on Day 28 will be repeated) 7 days ( $\pm 2$  days) after it was reached.

Should any subjects withdraw or be withdrawn from the study, all the early termination evaluations should be performed if possible, including samples for PD assessments if applicable.

Immunogenicity samples will be collected at the follow-up visits. The follow-up procedures are listed in the Study Events Flow Chart [Section 6](#).

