Subjects (including those who terminate early) will return on Days 14 and 28 for follow-up (FU) procedures (coagulation sample collection, thrombin time measurement, and immunogenicity sample collection) and to determine if any AE has occurred since the last study visit). Subjects who terminate the study early will be asked to continue aPTT and thrombin time monitoring as scheduled until Day 28.

Any subjects for whom aPTT and/or thrombin time did not reach  $\pm 10\%$  of the baseline value or within the normal range by Day 14, will return every 7 days ( $\pm 2$  days) until aPTT and thrombin time reach  $\pm 10\%$  of the baseline value or within

the normal range and for a FU visit (i.e., FU procedures and AE evaluation listed on Day 28 will be repeated) 7 days ( $\pm$  2 days) after it was reached.

The total planned duration of subject participation is approximately 56 days from screening to last FU.

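### Laboratory summaries leave out the Day 14 retest, the conditional weekly visits and early-termination samples, so recovery of aPTT and thrombin time is not summarised and an early leaver may have no post-dose value in them

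*SAP*

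**What the plan says.** SAP section 8.4 summarises numeric laboratory results by dose level, pooled placebo and time point, with change from baseline and, for aPTT, fold change. It then limits what enters: "Postdose unscheduled events or rechecks will not be included in summaries. Similarly early termination results will not be included in summaries". Baseline is the last result before the dose, "which may include unscheduled or recheck results, whichever is later". For shifts, "a shift table will be developed to compare the frequency of the results at baseline" with the corresponding post-dose results. That paragraph does not repeat the exclusion.

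For coagulation, Table 8.1 gives the Day 1 times as "Predose, 0.083, 0.25, 0.5, 1, 2, 4", then 24 h on Day 2, Day 14 and Day 28. Chemistry, haematology and urinalysis have one post-dose time, 24 h on Day 2. A footnote allows the Day 2 samples to be taken before discharge or at early termination.

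Further tests are compulsory when values have not recovered. Under Protocol 10.2.4, if aPTT or thrombin time is raised "at Day 14, both tests will be repeated". SAP section 3 restates that a subject whose aPTT or thrombin time has not come back to within 10% of baseline "or within the normal range by Day 14, will return every 7 days" until recovery, followed by a repeat follow-up visit 7 days later.

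SAP section 8 lists all results by subject, including rechecks, unscheduled and early-termination values. Table 14.3.4.3 lists out-of-range coagulation values with rechecks. Protocol 12.1.3 plans to summarise all clinical laboratory results and states no exclusion. SAP section 9 says that its analyses are aligned with the protocol.

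**The concern.** Leaving unscheduled results out of by-time-point tables is normal practice when they are stray values. Here many of them are not stray. The protocol requires the Day 14 retest and the weekly visits, and they occur only in subjects whose coagulation values have not recovered. Early-termination samples come only from subjects who left. The rule therefore removes values selectively from the subjects a safety reader most wants to follow.

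Safety and tolerability is the primary objective. Whether a late aPTT or thrombin-time prolongation resolves, and when, is a basic safety result for this product. As planned, a reader has to assemble it from listings. Thrombin time is the more exposed of the two tests, because the protocol flow chart schedules it after dosing only on Days 14 and 28.

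**Working it through.** **1. Scheduled coagulation points.** SAP Table 8.1, on study: 1 predose + 6 later on Day 1 + 1 at 24 h + 2 (Days 14 and 28) = 10. Protocol Table 3 also counts 10, at 3.5 mL each: 10 × 3.5 = 35 mL, its stated figure. Post-dose points: 10 − 1 = 9, all summarised. Protocol Table 3 covers the weekly sampling only in a footnote, outside the 10.

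**2. Conditional visits against Table 8.1.** Weekly visits fall nominally on Day 14 + 7k. If recovery is found on Day R, the repeat follow-up visit is on Day R + 7. Visits are assumed to be on the nominal day; the window is ±2 days.

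| Recovered on | Repeat visit | Days from 14 on with a Table 8.1 row | Days without a row |
|---|---|---|---|
| 21 | 28 | 14, 28 | 21 |
| 28 | 35 | 14, 28 | 21, 35 |
| 35 | 42 | 14, 28 | 21, 35, 42 |
| 42 | 49 | 14, 28 | 21, 35, 42, 49 |

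In every row of the table the Day 14 retest is also left out, by the explicit rule on rechecks. If recovery comes by Day 28, the Day 28 value is summarised, but nothing gives the day of recovery. If it comes after Day 28, the last value in the summaries is an unrecovered one. The criterion of ±10% of baseline or normal range appears in none of the planned laboratory summaries.

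**3. Early leavers.** Chemistry, haematology and urinalysis have 1 scheduled post-dose point. For a subject who leaves before 24 h, that sample is the early-termination sample. Table 8.1 assigns it to Day 2 and the next rule drops it: 1 − 1 = 0 post-dose values in the summaries, and the dose level falls from n = 4 to n = 3. Early terminators do return on Days 14 and 28, but those visits cover coagulation, thrombin time and immunogenicity, not these panels.

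**4. Weight of one subject.** Active dose level: 1/4 = 25%. Pooled placebo: 2 + 1 + 1 + 1 = 5, so 1/5 = 20%. The documents give no expected rate of Day 14 non-recovery or early withdrawal, so the number affected cannot be projected and may be zero.

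**5. Protocol against SAP.** Protocol 12.1.3 summarises all laboratory results; SAP 8.4 summarises a subset; SAP section 9 records no change. These three do not agree.

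**The case against.** The strongest case for the plan is that by-time-point tables should use scheduled values. Leaving out the retest keeps the raised Day 14 value in the table instead of letting a normal retest replace it. The acute course is fully covered. All excluded values are listed, and with four active subjects per dose each course can be read by eye. Table 14.3.4.5 shows every time point for any subject and test with a value judged clinically significant. Such values are generally captured as adverse events, which are counted by dose level. Escalation rests on review of blinded data through Day 14, not on the final tables.

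Most of this stands, and it rules out several stronger readings that a reader might infer:

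- That the abnormal course is never summarised. Nine post-dose coagulation points are, including the triggering Day 14 value.
- That the tables must understate the worst change. Nothing in the documents shows that later values would be worse.
- That all extra visits are lost. A weekly visit due on Day 28 coincides with a scheduled row.
- That allowing rechecks for baseline but not after dosing is a fault. A pre-dose recheck is simply the last value before a single dose.
- That the SAP expressly excludes the weekly visits, or expressly applies the exclusion to shift tables. It does neither; both are inferences. The weekly visits are not classed at all, and no rule gives them a place.

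The listings do not close the gap. Table 14.3.4.3 holds out-of-range values and their rechecks, so a normal value at a weekly visit is not assured a place there. Table 14.3.4.5 depends on the investigator's judgement. SAP section 8 provides reduced denominators for missing data, but an early-termination sample that was taken is not missing.

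**Conclusion.** The point holds in limited form. By explicit text, the Day 14 retest and early-termination results are left out of the laboratory summaries. By the absence of any row or rule, so are the weekly and repeat visits on nominal Day 21 and after Day 28. No planned summary says how many subjects per dose level had not recovered at Day 14, or when they recovered. An early leaver may have no post-dose chemistry, haematology or urinalysis value in any summary; this is certain for the by-time-point tables and depends, for the shift tables, on whether they follow the same rule.

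One affected subject is 25% of an active dose level. That is the subject's share of the group, not an estimate of bias in any result. The narrowing from the protocol is undeclared. The sponsor should correct this before unblinding, but it does not threaten the conduct of the trial, and no data are lost because all results are listed.

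**What to change.** Keep the by-time-point summaries of scheduled values as they are, and make these changes in the SAP:

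1. State how the weekly and repeat follow-up visits are classed, and whether the by-time-point shift rows use scheduled results only.
2. Add to the shift tables and the aPTT fold-change table a row labelled as the worst post-dose value, using all post-dose results: scheduled, recheck, unscheduled, conditional follow-up and early termination. Define the direction of worst for each test.
3. Add, by dose level and pooled placebo, the number of subjects whose aPTT or thrombin time had not returned to within ±10% of baseline or the normal range at Day 14, with the day of recovery, or the last day sampled if recovery was not seen. Name the baseline used. The protocol refers this criterion to check-in, the SAP takes coagulation baseline on Day 1, and thrombin time is sampled at check-in; these must be reconciled.
4. Reconcile the Table 8.1 early-termination footnote with the exclusion, and say whether early terminators' Day 14 and Day 28 results are summarised. SAP sections 8.5 and 8.6 pair the same footnote with the same exclusion and need the same check.
5. Record the exclusion in section 9.

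The cost is SAP wording, one row in existing tables and one short table, with no change to sampling or clinical rules. The downside is that a worst-value row mixes time points, and subjects with more visits have more chances of an extreme value, so it must be labelled. For aPTT the worst value may often be the acute peak (about 15 to 30 minutes in the baboon data), so the recovery count carries most of the late information.

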## 8.5 Vital Signs

Single measurements of systolic and diastolic blood pressure, heart rate, body temperature, and respiratory rate will be obtained in supine position at the following time points:

**Table 8.2 Vital Signs Data Time Points**

Measurement	Period	Day	Hour
Blood Pressure / Heart Rate/ Respiratory Rate / Body Temperature	Screen		
	1	1	Predose, 0.25, 0.5, 1, 2, 4
		2*	24

\*Prior to discharge from CRU or at early termination from the study.

Vital signs tests will be summarized by dose level, pooled placebo, and time point. Change from baseline will be summarized in a similar way. Baseline is defined as the result closest and prior to the dose on Day 1, which may include unscheduled or recheck results, whichever is later. Postdose unscheduled events or rechecks will not be included in summaries. Similarly early termination results will not be included in summaries.

## 8.6 Electrocardiogram

Single 12-lead ECGs (i.e., HR, PR, QRS, QT, and QTcF [i.e., QT corrected for heart rate using Fridericia's correction]) will be measured at the following time points:

**Table 8.3 12-Lead Electrocardiogram Data Time Points**

Parameter	Period	Day	Hour
HR, PR, QRS, QT, QTcF	Screen		
	1	1	Predose
		2*	24

\*Prior to discharge from CRU or at early termination from the study.

ECGs will be summarized by dose level, pooled placebo, and time point. Change from baseline will be summarized in a similar way. Baseline is defined as the result closest and prior to the dose on Day 1, which may include unscheduled or recheck results, whichever is later. Postdose unscheduled events or rechecks will not be included in summaries. Similarly early termination results will not be included in summaries.

The QTcF values that are > 450 ms and increase from baseline > 30 ms, will be flagged in the data listings.

## 8.7 Concomitant Medications

All concomitant medications recorded during the study will be coded with the WHO Dictionary Version 01-Mar-2018 or a later version if available and listed.

## 8.8 Physical Examination

Full physical examination will be performed at screening. A symptom-driven physical examination will be performed at check-in and FU or may be performed at other scheduled times, at the PI's or designee's discretion. Abnormal findings will be reported as medical history or adverse events. All data found in the CRF will be listed.

## 8.9 Injection Site

Injection and needle puncture site reactions for drug administration will be evaluated at the following time points:

**Table 8.4 Injection Site Reaction**

Parameter	Period	Day	Hour
Site Reaction	Screen		
	1	1	Predose, 1
		2*	24

\*Prior to discharge from CRU or at early termination from the study.

Abnormal findings will be reported as adverse events.

## 9. SUMMARY OF CHANGES FROM PROTOCOL-PLANNED ANALYSIS

The analyses described in this SAP are aligned with those analyses described in the protocol.

## 10. SUMMARY TABLES AND FIGURES

Summary tables and figures are numbered following the International Conference on Harmonization (ICH) structure but may be renumbered as appropriate during the compilation of the tables and figures for the CSR. Note that summary tables and figures will be generated using SAS® Version 9.3 or higher.

### 10.1 In-text Summary Tables and Figures

The following is a list of table and figure titles that will be included in the text of the CSR. Tables and figures will be numbered appropriately during compilation of the CSR.

#### Section 10:

Table 10-1 Subject Disposition Summary (Safety Population)

Section 11:

Table 11-1 Demographic Summary (Safety Population)

**Pharmacodynamics**

Table 11-2 Summary of APC-PCI Pharmacodynamics Following Administration of a Single IV Dose of 0.5, 1.0, 2.0, and 4.0 mcg/kg E-WE Thrombin

Figure 11-1 Mean Plots of APC-PCI Pharmacodynamics Following Administration of a Single IV Dose of 0.5, 1.0, 2.0, and 4.0 mcg/kg E-WE Thrombin

**Immunogenicity**

Table 11-3 Summary of Anti- E-WE Thrombin Plasma ADA Following Administration of a Single IV Dose of 0.5, 1.0, 2.0, and 4.0 mcg/kg E-WE Thrombin

Table 11-4 Summary of Anti-WT Thrombin Serum ADA Following Administration of a Single IV Dose of 0.5, 1.0, 2.0, and 4.0 mcg/kg E-WE Thrombin

Section 12:

Table 12-1 Adverse Event Frequency by Dose Level - Number of Subjects Reporting the Event (% of Subjects Dosed) (Safety Population)

**10.2 Section 14 Summary Tables and Figures**

The following is a list of table and figure titles that will be included in Section 14 of the CSR. Table and figure titles may be renumbered as appropriate during the compilation of the CSR.

**14.1 Demographic Data Summary Tables**

Table 14.1.1 Subject Disposition Summary (Safety Population)

Table 14.1.2 Demographic Summary (Safety Population)

**14.2 Pharmacodynamic/Immunogenicity Data Summary Tables and Figures**

**Pharmacodynamic Tables**

**14.2.1 Plasma APC-PCI Tables**

Table 14.2.1.1 Plasma APC-PCI Levels (<units>) Following a Single IV Dose of 0.5 mcg/kg E-WE Thrombin (Pharmacodynamic Population)

- Table 14.2.1.2 Plasma APC-PCI Levels (<units>) Following a Single IV Dose of 1.0 mcg/kg E-WE Thrombin (Pharmacodynamic Population)
- Table 14.2.1.3 Plasma APC-PCI Levels (<units>) Following a Single IV Dose of 2.0 mcg/kg E-WE Thrombin (Pharmacodynamic Population)
- Table 14.2.1.4 Plasma APC-PCI Levels (<units>) Following a Single IV Dose of 4.0 mcg/kg E-WE Thrombin (Pharmacodynamic Population)
- Table 14.2.1.5 Plasma APC-PCI Levels (<units>) Following Placebo Administrations of E-WE Thrombin (Pharmacodynamic Population)

### **Immunogenicity Tables**

#### **14.2.2 Anti-E-WE and Anti-WT Thrombin Antibody**

- Table 14.2.2.1 Plasma E-WE Thrombin ADA Detection Summary by Collection Time and Dose Level Following Administration of a Single IV Dose of 0.5, 1.0, 2.0, or 4.0 mcg/kg E-WE Thrombin - Number of Subjects (% Total Subjects)
- Table 14.2.2.2 Serum Anti-WT Thrombin ADA Detection Summary by Collection Time and Dose Level Following Administration of a Single IV Dose of 0.5, 1.0, 2.0, or 4.0 mcg/kg E-WE Thrombin - Number of Subjects (% Total Subjects)
- Table 14.2.2.3 Summary of Titers for Plasma Anti-E-WE Thrombin Antibody
- Table 14.2.2.4 Summary of Titers for Serum Anti-WT Thrombin Antibody
- Table 14.2.2.5 Plasma Anti-E-WE Thrombin Antibody Duration by Dose Level Following Administration of a Single IV Dose of 0.5, 1.0, 2.0, or 4.0 mcg/kg E-WE Thrombin
- Table 14.2.2.6 Serum Anti-WT Thrombin Antibody Duration by Dose Level Following Administration of a Single IV Dose of 0.5, 1.0, 2.0, or 4.0 mcg/kg E-WE Thrombin

### **Pharmacodynamic Figures**

#### **14.2.3 Plasma APC-PCI Figures**

- Figure 14.2.3.1 Mean Plasma APC-PCI Levels Versus Time Profiles Following a Single IV Dose of 0.5, 1.0, 2.0, 4.0 mcg/kg, or

- Placebo E-WE Thrombin (Linear Scale) (Pharmacodynamic Population)
- Figure 14.2.3.2 Median Plasma APC-PCI Levels Versus Time Profiles Following a Single IV Dose of 0.5, 1.0, 2.0, 4.0 mcg/kg, and Placebo E-WE Thrombin (Linear Scale) (Pharmacodynamic Population)

#### **14.2.4 Immunogenicity Figures**

- Figure 14.2.4.1 Summary of Titers for Plasma Anti-E-WE Thrombin Antibody by Treatment – Line Plot (Mean  $\pm$  SD) for Confirmatory Test Results
- Figure 14.2.4.2 Summary of Titers for Plasma Anti-E-WE Thrombin Antibody by Treatment – Line Plot (Mean) for Confirmatory Test Results
- Figure 14.2.4.3 Summary of Titers for Serum Anti-WT Thrombin Antibody by Treatment – Line Plot (Mean  $\pm$  SD) for Confirmatory Test Results
- Figure 14.2.4.4 Summary of Titers for Serum Anti-WT Thrombin Antibody by Treatment – Line Plot (Mean) for Confirmatory Test Results

### **14.3 Safety Data Summary Tables**

#### **14.3.1 Displays of Adverse Events**

- Table 14.3.1.1 Treatment-Emergent Adverse Event Frequency by Dose Level – Number of Subjects Reporting the Event (% of Subject Dosed) (Safety Population)
- Table 14.3.1.2 Treatment-Emergent Adverse Event Frequency by Dose Level – Number of Adverse Events (% of Total Adverse Events) (Safety Population)
- Table 14.3.1.3 Treatment-Emergent Adverse Event Frequency by Dose Level, Severity, and Relationship to Study Drug – Number of Adverse Events (Safety Population)

#### **14.3.2 Listings of Deaths, other Serious and Significant Adverse Events**

- Table 14.3.2.1 Serious Adverse Events (Safety Population)

#### **14.3.3 Narratives of Deaths, other Serious and Certain other Significant Adverse Events**

#### **14.3.4 Abnormal Laboratory Value Listing (each patient)**

- Table 14.3.4.1 Out-of-Range Values and Recheck Results – Serum Chemistry (Safety Population)
- Table 14.3.4.2 Out-of-Range Values and Recheck Results – Hematology (Safety Population)
- Table 14.3.4.3 Out-of-Range Values and Recheck Results – Coagulation (Safety Population)
- Table 14.3.4.4 Out-of-Range Values and Recheck Results – Urinalysis (Safety Population)
- Table 14.3.4.5 Clinically Significant Laboratory and Corresponding Results (Safety Population)

